## 1.3 Schedule of Activities

Activity / Assessment	Screening / Baseline	Intervention Period (in cycles of 3 weeks)									EoT	Safety Follow up / Discontinuation	Survival Follow-Up / EoS / 1-Year Follow-Up	Notes
	Day -56 to Day -1	Cycle 1 (21 days)		Cycle 2 (21 days)		Cycle 3 and subsequent cycles (21 days)					Within 14 days after decision to withdraw IMP	30 days after the last dose	After Safety Follow-Up, every 3 months, up to 1-year Site Visit or by Telephone	
Cycle Day		1	8	15	1	8	15	1	8	15				
Visit Window		± 3 days			± 3 days			± 3 days				- 3 to + 7 days	± 1 month	
Study Site Visits	X	X	X	X	X	X	X	X	X	X	X	X	X	At the Investigator's discretion, additional assessments may be performed at unscheduled time points if clinically indicated.
Written informed consent	X													
Inclusion and Exclusion Criteria	X													Recheck clinical status before 1st dose of study intervention. Screening labs for eligibility should be performed within 7 days prior to C1D1.
Demography	X													
Medical history	X													
HIV Screening	X													HIV testing is optional unless required locally.
Hepatitis B and C	X													

Activity / Assessment	Screening / Baseline	Intervention Period (in cycles of 3 weeks)									EoT	Safety Follow up / Discontinuation	Survival Follow-Up / EoS / 1-Year Follow-Up	Notes
	Day -56 to Day -1	Cycle 1 (21 days)			Cycle 2 (21 days)			Cycle 3 and subsequent cycles (21 days)			Within 14 days after decision to withdraw IMP	30 days after the last dose	After Safety Follow-Up, every 3 months, up to 1-year Site Visit or by Telephone	
Cycle Day		1	8	15	1	8	15	1	8	15				
Visit Window		± 3 days			± 3 days			± 3 days				- 3 to + 7 days	± 1 month	
Pregnancy Test (women of child bearing potential only)	X	X			X			X			X	X		Serum test at Screening, urine test thereafter. See Section 7.1 for EoT assessment due to occurrence of pregnancy
Physical examination	X	X	X	X	X		X	X		X	X	X		Symptom directed-physical examinations will be performed as clinically indicated per Investigator's judgment.
Vital signs	X	X	X	X	X		X	X		X	X			Includes height (collect at Screening only) and weight.
Standard 12-lead ECG including QTc	X	X			X					X				As triplicates. ECG assessment should be performed within 60 minutes prior to predose PK blood sample collection (See Appendix 4).
ECOG PS	X	X			X			X		X	X			

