9.7 Definition of On-treatment Period

The on-treatment period is defined as the time from the first dose of study treatment day to the last administration day of study treatment + 30 days, or the cut-off date or death or the start day of subsequent anti-cancer drug therapy - 1 day, whichever occurs first.

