UNK	> Treatment start (month and year) and <= Treatment end + 30 days (month and year)		After treatment start	Concomitant		
<= Treatment start (date)			Before treatment start	Previous		
<= Treatment start (date)			After treatment start	Previous and concomitant		
> Treatment start (date) and <= Treatment end + 30 days (date)			After treatment start	Concomitant		

UNK = Unknown

Dates of study treatment

Start date of study treatments:

- No imputation will be done.

End date of study treatments:

- In case the last date of study drug is missing or incomplete the date of last administration of study drug will be taken from the treatment termination eCRF pages.
- If the last date of study drug is completely missing and there is no End of Treatment eCRF page and no death date the participant should be considered to be ongoing and use the cut-off date for the analysis as the last dosing date
- If the last date of study drug is completely or partially missing and there is EITHER an End of Treatment eCRF page OR a death date available (within the cut-off date) then imputed last dose date is:
 - 31DECYYYY, if only Year is available and Year < Year of min (EOT date, death date)

- Last day of the month, if both Year and Month are available and Year = Year of min (EOT date, death date) and Month < the month of min (EOT date, death date)
- min (EOT date, death date), for all other case

Death date

In general, missing or partial death dates will not be imputed. However, for the purpose of survival analyses, partially missing death dates will be imputed as follows: if only the day is missing, the death date will be imputed to the maximum of the (non-imputed) day after the date of last contact (see Section 9.6) and the 15th day of the month.

Tumor assessments

All investigation dates (e.g. X-ray, CT scan) must be completed with day, month and year.

If there are multiple scan dates associated with an evaluation, i.e., radiological assessments occur over a series of days rather than the same day, the choice of date of assessment could impact the date of progression and/or date of response. If there are multiple scan dates associated with an evaluation, the earliest of the scan dates associated with the evaluation will be used as the date of assessment.

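### SAP 9.8 gives an impossible last-dose date when the month is known and the year is earlier than that of EoT or death; a one-clause fix of small impact

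*SAP*

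**What the plan says.** SAP 9.8, under the end date of study treatments, first looks elsewhere for the date: "the date of last administration of study drug will be taken from the treatment termination eCRF pages". The imputation is the fallback. It applies when the last-dose date is wholly or partly missing and an EoT page or a date of death exists by the cut-off, and it has three branches:

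1. Year-only branch: "31DECYYYY, if only Year is available and Year < Year of min (EOT date, death date".
2. Known-month branch: "Last day of the month, if both Year and Month are available and Year = Year of min (EOT date, death date". A further condition is that the recorded month must come before that of the reference date.
3. Catch-all: "min (EOT date, death date), for all other case".

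The result feeds other definitions. SAP 9.8 uses imputed dates for durations. SAP 9.7 runs the on-treatment period to "the last administration day of study treatment + 30 days", or to death, cut-off or the day before subsequent anti-cancer drug therapy if earlier. SAP 15.3.1 counts deaths within 30 and within 90 days of last dose.

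**The concern.** The branches leave one case without its own rule: year and month recorded, year earlier than that of the reference date. Branch 1 excludes it because the month is known. Branch 2 excludes it because the years differ. The catch-all then assigns a date that the record itself rules out.

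Two comparisons show that this is a slip and not a choice. Recording the month gives a worse date than leaving it out. And the same pattern within one calendar year is handled properly. Table 2 of the same section, for medication end dates, already compares month and year together.

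A last-dose date that is too late lengthens duration of therapy, lowers relative dose intensity and shortens the apparent interval from last dose to death. With about 22 and 20 participants per cohort, one misclassified participant moves a percentage by 1/22 = 4.5 or 1/20 = 5 points.

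**Working it through.** The plan states no figure on this point, so there is nothing to reproduce. The check applies the three branches literally. M denotes the earlier of the EoT and death dates. All calendar dates are illustrative.

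**Branch by branch**

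| Recorded last dose | M | Branch met | Date assigned | Latest date possible | Overshoot |
|---|---|---|---|---|---|
| 2021 only | 10JAN2022 | 1 | 31DEC2021 | 31DEC2021 | 0 days |
| --/DEC/2021 | 10JAN2022 | 3 | 10JAN2022 | 31DEC2021 | 10 days |
| --/NOV/2021 | 10DEC2021 | 2 | 30NOV2021 | 30NOV2021 | 0 days |
| --/DEC/2021 | 20DEC2021 | 3 | 20DEC2021 | 20DEC2021 | 0 days |

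Only the second row, where the year changes between the recorded month and M, goes wrong.

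**How often**

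The gap from last dose to EoT is not fixed by the plan. The Protocol's Schedule of Activities places the EoT visit "Within 14 days after decision to withdraw IMP"; Protocol 4.1 counts the 14 days from the last dose. Protocol 6.6.2 allows a tepotinib hold of up to 21 days. An upper gap is therefore 21 + 14 = 35 days. Taking every day of 2021 as the true last dose, masking the day and applying the rule:

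| Assumed gap | Month-only records affected | Overshoot |
|---|---|---|
| 7 days | 7/365 = 1.9% | 1-7 days |
| 14 days | 14/365 = 3.8% | 1-14 days |
| 21 days | 21/365 = 5.8% | 1-21 days |
| 35 days | 35/365 = 9.6% | 5-35 days |

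These are shares of month-only records, not of participants. One such record in the trial implies 0.02 to 0.10 affected participants.

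**Effect on exposure**

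SAP 13 defines tepotinib duration as (last day - first day + 1)/7 weeks and relative dose intensity as actual over intended dose per 3-week cycle. Assume 500 mg daily from 01SEP2021 to 31DEC2021, which is 122 days.

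- Last dose 31DEC2021: 122/7 = 17.4 weeks; relative dose intensity 100%.
- Last dose imputed as 10JAN2022: 132/7 = 18.9 weeks; relative dose intensity 100 x 122/132 = 92.4%.

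**Effect on the death tables**

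If a participant has a death date and no EoT page, M is the date of death. With --/NOV/2021 and death on 10JAN2022, the imputed last dose is the day of death, so the death counts as within 30 days. The record shows at least 10JAN2022 - 30NOV2021 = 41 days.

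**Effect on the safety window**

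Take --/DEC/2021 with EoT on 10JAN2022. With 31DEC2021 the on-treatment period would end 30 days later, on 30JAN2022. With 10JAN2022 it ends on 09FEB2022, 10 days later. Protocol 8.3.1 collects AEs until the Safety Follow-up Visit, 30 days (-3 to +7) after last dose. On schedule that is no later than 31DEC2021 + 37 days = 06FEB2022, so at most 7 of the 10 added days carry routine AE collection.

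**The case against.** The strongest reply is that this is a third-level fallback that may touch nobody. The termination page is consulted first; SAP 13 also refers to the administration pages for the last date with a dose above zero; Protocol 6.4 requires intervention stop dates in the eCRF; and a data review meeting precedes each lock. The catch-all is explicit, so programmers are not left guessing, and it never passes EoT or death. All analyses are descriptive. All of this stands and sets the size of the point. It does not make the assigned date right.

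A reader might infer more than the documents support:

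- *That the safety window stretches 50 to 71 days past the last possible dose and turns many later events into TEAEs.* The 71 days come from a 41-day overshoot plus 30. With EoT as the reference, a 41-day overshoot needs a gap of at least 41 days, beyond the 35 that the hold and visit timing allow. Even the 50 days (a 20-day overshoot plus 30) would add little, because routine collection stops at the Safety Follow-up Visit. SAP 9.7 closes the period at death, cut-off or new drug therapy, and SAP 9 takes the later of the two drugs' dates, so an error in one drug counts only by the amount it exceeds the other.
- *That about 10% of such records are affected.* That is the ceiling, with every gap at 35 days.
- *That the primary result is at risk.* SAP 14.1.1 derives response from tumor assessments up to progression or subsequent therapy, not from the last-dose date. The end of treatment also serves as a floor for a partial start date of subsequent therapy, but that needs a second partial date, and SAP 9.8 ties it to sensitivity analyses.

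**Conclusion.** The rule is wrong as written for one case, and no other section corrects it. A last-dose date with a known month in an earlier year than the EoT or death date receives a date later than the record permits.

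The impact is small: about 2-10% of month-only records for gaps of 7 to 35 days, among at most 48 participants, and only where the termination page gives no full date. The overshoot is up to about 35 days when EoT is the reference and longer only when a later death date is. These figures assume that the EoT date is the visit date, that the visit is on schedule, that last doses are spread evenly over the year, and that the EoT date follows the stopping of the drug concerned.

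Duration of therapy, relative dose intensity and the 30- and 90-day death flags are mainly exposed. The effect on TEAEs and worst on-treatment values is limited, and the derivation of objective response is unaffected.

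**What to change.** In the second branch of SAP 9.8, replace the two separate conditions (same year, earlier month) by one: use the last day of the recorded month whenever the recorded year and month, taken together, precede the year and month of the earlier of the EoT and death dates. The catch-all then covers a completely missing date, a record in the same month as the reference date, and a year-only record in the same year.

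With this wording --/DEC/2021 and EoT 10JAN2022 gives 31DEC2021. Year-only, same-year earlier-month and same-month records keep their present dates. The cost is one clause in the SAP and one programming condition; there is no analytic downside.

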9.9 Tumor Evaluation and Adjudication

Missing data from scheduled Tumor assessments not performed will not be imputed. Evaluable Tumor assessments are defined as those with overall response CR, PR, SD or PD. Data from non-evaluable (NE) Tumor assessments will be used in the derivation of endpoints in accordance with [Eisenhauer et al., \(2009\)](#).

In case IRC assessments are performed only the response assessments which are flagged as accepted after adjudication will be taken over to ADaM datasets and will be analyzed. In case of a missing adjudication flag for a response assessment and earliest image dates are equal, the assessment of reader 1 (the reader who completed baseline first) will be taken for analysis. Otherwise the assessment for the reviewer who reviewed the record with the earliest image date will be analyzed. Analyses of tumor sizes will be based only on assessments of the reader whose assessment was accepted at baseline.

10 Study Participants

The subsections in this section include specifications for reporting participant disposition and study treatment/study discontinuations. Additionally, procedures for reporting protocol deviations are provided.

10.1 Disposition of Participants and Discontinuations

The number and percentage of participants in each of the below disposition categories will be presented by cohort, by assigned dose level of tepotinib and overall. Percentages will be presented with respect to the number of participants in FAS/SAF analysis set.

Participant disposition will be summarized as follows:

- Number of participants in each analysis set (SCR, SAF, DLT, PKAS, IMAS)
- Number of participants who discontinued from the study prior to treatment overall and grouped by the main reason (e.g. the failed specific inclusion or exclusion criteria, withdrawal of consent)

The end of treatment status will be summarized by:

- Number of participants who received at least one dose of study treatment
- Number and percentage of participants who have permanently discontinued study treatment
- Number and percentage of participants with study treatment ongoing
- Number and percentage of participants who did not receive tepotinib
- Number and percentage of participants with tepotinib treatment ongoing

- Number and percentage of participants who permanently discontinued tepotinib treatment (overall and by primary reason)
- Number and percentage of participants who did not receive cetuximab
- Number and percentage of participants with cetuximab treatment ongoing
- Number and percentage of participants who permanently discontinued cetuximab treatment (overall and by primary reason)

The end of study status will be summarized by:

- Number and percentage of participants with any study treatment ongoing
- Number and percentage of participants off-treatment and in safety or survival follow-up
- Number and percentage of participants who discontinued the study (overall and by primary reason)

For each participant in the FAS/SAF analysis set, the first and last dosing date for each study component (including reason for treatment discontinuation) and study discontinuation date (including reason for study discontinuation) will be listed.

Additionally, the number of participants enrolled in each analysis population will be provided overall, by region, by country within region and by site. Results will be presented by cohort and by assigned dose level of tepotinib. This information will also be provided for each participant in the FAS/SAF analysis set in a listing.

Disposition of participants will be presented in a CONSORT Flow Diagram.

10.2 Protocol Deviations / Exclusion from Analysis Populations

10.2.1 Important Protocol Deviations

Important protocol deviations (IPDs) are protocol deviations that might significantly affect the completeness, accuracy, and/or reliability of the study data or that might significantly affect a participant's rights, safety, or well-being.

Important protocol deviations include, but are not limited to:

- Participants enrolled and dosed on the study who did not satisfy enrolment criteria
- Participants who are not compliant with treatment: overdose, dose modifications not as per protocol, incorrect dose, etc.
- Participants who receive a prohibited concomitant medication
- Failure to collect data necessary to interpret primary endpoints
- Failure to collect necessary key safety data
- Deviation from Good Clinical Practice (GCP)

- Any other protocol deviation that might significantly affect the completeness, accuracy, and/or reliability of the study data or that might significantly affect a participant's rights, safety, or well-being.

All important protocol deviations are documented in SDTM datasets whether identified for all participants by either medical review processes or programming and confirmed prior to or at the Data Review Meeting at the latest.

The protocol deviations recorded in the Clinical Trial Management System (CTMS) may utilize different terminology. The table below displays how the terminology used in CTMS translates to the terminology used in the IAP, the SDTM and ADaM datasets, and ultimately the CSR:

CTMS	IAP	SDTM	ADaM
Non-important	Non-important (only for protocol deviations related to COVID-19)	Only protocol deviations related to COVID-19 are included	Only protocol deviations related to COVID-19 are included
Important	Important	Flagged with PDEVXXX code	Flagged with PDEVXXX code
Relevant	Relevant for PK	Mapped to Important	Mapped to Important

A full list of potential protocol deviations including definition and categorization is maintained by Covance in the “Study Specific Protocol Deviation List” attached to the Protocol Deviation Management Plan.

A frequency table (split by deviations from the inclusion and exclusion criteria as well as all other deviations) and a listing of important protocol deviations will be provided based on the SAF analysis set.

10.2.2 Reasons Leading to the Exclusion from an Analysis Population

Participants who have relevant protocol deviations or important events affecting PK will be excluded from PKAS.

11 Demographics and Other Baseline Characteristics

Demographic data and other baseline characteristics will be presented for the FAS/SAF analysis set using summary statistics for continuous variables and frequency statistics (i.e. counts and percentages) for categorical variables. Results will be presented as indicated in Section 10.

Listings showing demographic data and other baseline characteristics will be presented for the FAS.

11.1 Demographics

Demographic characteristics will be summarized descriptively using the following information from the Screening/Baseline Visit eCRF pages.

- Sex: male, female, undifferentiated
- Race: white, black or African American, Asian, American Indian or Alaska Native, Native Hawaiian or Other Pacific Islander, not collected at this site, more than one race, other, missing
- Ethnicity:
 - Hispanic or Latino / Not Hispanic or Latino
- Age (years)
- Age categories:
 - < 65 years,
 - \geq 65 years
 - 65-74,
 - 75-84,
 - \geq 85 years
- Pooled Regions: Europe, North America
- Country (e.g.: Belgium, Czech Republic, France, Italy, Russia, Spain, United Kingdom, USA)

Specifications for computation:

- Age [years]:
 - Age = (01.JAN.YEAR informed consent date for screening – 01.JAN.YEAR of birthdate + 1) / 365.25.

The integer part of the calculated age will be used for reporting purposes.

- Site codes will be used for the determination of the participant's pooled region and country.
- Participants with more than one race will be summarized in the “more than one race” category.

11.2

Medical History

The medical history will be summarized from the “Medical History” eCRF page, using the most recent MedDRA version at time of database lock, preferred term as event category and system organ class (SOC). Each participant will be counted only once within each PT or SOC.

Medical history will be displayed in terms of frequency tables ordered by primary SOC in alphabetic order and PT in alphabetical order.

A listing will be provided with SOC term, PT term, toxicity grade and whether related to the study condition.

11.3

Disease History

Information on disease history is collected during the screening visit on the “Disease History” eCRF page. Data will be summarized and listed as follows:

- Site of Primary Tumor by International Classification of Diseases for Oncology (ICD-O) codes will be translated into text for presentation in outputs
- Time since initial cancer diagnosis (years) = (date of start of study treatment – date of initial cancer diagnosis + 1) / 365.25
- Time since documented locally advanced, inoperable or metastatic disease diagnosis (years) = (date of start of study treatment – date of documented locally advanced, inoperable or metastatic disease diagnosis + 1) / 365.25
- Tumor histopathologic / cytologic type: Adenocarcinoma / Mucinous adenocarcinoma/ Not differentiated cancer/ Neuroendocrine tumor/ Other
- Disease stage at initial diagnosis
- Disease stage at study entry
- TNM classification at initial diagnosis
- TNM classification at study entry

Incomplete dates for initial cancer diagnosis and documented locally advanced, inoperable or metastatic disease diagnosis will be handled as specified in Section 9.8.

11.4

Baseline Tumor Assessment

Information collected by the Investigator on the baseline tumor assessment collected at the screening visit on the “Tumor Assessment (according to RECIST 1.1)” eCRF pages and “Sum of Diameters (according to RECIST 1.1)” eCRF page will be presented. Summaries will be presented for the following:

- Target lesions (by investigator)
 - Number of target lesions
 - Sum of diameters (sum of longest diameters for non-nodal lesions, short axis for nodal lesions)
 - Type: Primary / Recurrence, Node, Metastasis
 - Site
- Non-target lesions (by investigator)
 - Number of participants with at least one non-target lesion
 - Number of non-target lesions
 - Type: Primary / Recurrence, Node, Metastasis
 - Site

Tumor information based on Investigator that is collected during the study will be listed.

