#### Age

1. Are  $\geq 18$  years of age (or having reached the age of majority according to local laws and regulations, if the age of majority is  $> 18$  years of age) at the time of signing the informed consent.

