## Study Assessments and Procedures

- Study assessments and procedures and their timing are summarized in the SoA (Section 1.3). A summary of key study activities on Day 1 of Cycles 1 and 2 is provided in [Appendix 4](#).
- No protocol waivers or exemptions are allowed.
- Immediate safety concerns are discussed with the Sponsor immediately upon occurrence or awareness to determine if the participant should continue or discontinue study intervention.
- Adherence to the study design requirements, including those specified in the SoA (Section 1.3), is essential and required for study conduct.
- All screening evaluations will be completed and reviewed to confirm that potential participants meet all eligibility criteria. Laboratory tests for eligibility should be performed within 7 days prior to C1D1. The Investigator will maintain a screening log to record details of all participants screened, to confirm eligibility, and if applicable, record reasons for screening failure.
- Prior to performing any study assessments that are not part of the participant's routine medical care, the Investigator will obtain written informed consent as specified in [Appendix 2](#).
- Procedures conducted as part of the participant's routine medical care (e.g., blood count) and obtained before signing of the ICF may be used for Screening or Baseline purposes provided the procedures met the protocol-specified criteria and were performed within the time frame defined in the SoA.
- A maximum of approximately 250 mL of blood will be collected in any one-month period from each participant in the study, including any extra assessments that may be required.
- Date of birth, sex (gender), race, and ethnicity will be collected only where allowed by local law/regulations.

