### **9.2 Sample Size Determination**

The number of participants to be screened is expected to be around 342 participants to account for the described heterogeneity for *MET* amplification in the planned setting (Pietrantonio 2017; Pietrantonio 2015; Raghav 2016; Liu 2019; Mohan 2014; Siravegna 2015; Morelli 2014; Montagut 2018; LC-SCRUM, ASCO 2019 [Nakamura 2019]).

In total, a maximum of 48 participants are planned to be assigned to study intervention such that approximately 22 (Cohort A) and 20 (Cohort B) participants will be treated at RP2D. The 42 participants will be under the same dose level. The sample size calculation of 42 participants is based on the full analysis set (FAS).

The aim is to have 22 participants treated with the RP2D of tepotinib for 2L line treatment (Cohort A) and 20 participants treated with the RP2D for the 3L+ treatment (Cohort B) with at least 6 participants in the safety run-in period, irrespective of cohort.

It is anticipated that 6 eligible participants irrespective of therapy line, will be enrolled into the first part of the study for the determination of RP2D of tepotinib depending on DLTs observed. If 250 mg tepotinib is to be used the number of participants enrolled for the determination of RP2D will increase up to 12 (See Section 9.4.2.1).

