Subgroup analyses will be performed on the primary efficacy endpoint OR and the secondary efficacy endpoints DoR/PFS/OS as defined in [Table 1](#). All subgroup analyses will be exploratory, no adjustment for multiplicity will be performed. Endpoints for which subgroup analyses will be performed can be found in [Section 14](#). In case of low number of participants within a subgroup level (< 5 participants), levels will be pooled when meaningful.

For the definition of subgroup levels, data as documented in the electronic case report form (eCRF) or provided in the SDTM datasets will be taken. The category “missing” will not be included in any subgroup analysis.

Table 1. Subgroups

Subgroup	Subgroup level	Definition/ Derivation
Treatment line	
• 2nd line (Cohort A)• 3rd line• 4th line• 5th + line	CRF: PRIOR ANTI-CANCER DRUG THERAPIES DETAILS: Regimen number
Site location (Cohort B)	
• ACCRU sites• Other US sites	
Mutations in the extracellular domain of EGFR	
• Yes• No	The following mutations are of relevance and should be taken into account: F404, T414, V441, S442, I462, S464, G465, K467, K489, I491, S492
MET amplification (if available)	
• Focal• Non-focal	
MET amplification	
• Liquid• Tissue	CRF: TISSUE BIOPSY FOR MET

		AMPLIFICATION: MET amplification result
Prior EGFR therapy	
 • Panitumumab • Cetuximab 	
Time since last EGFR therapy in months	
 • 1 • 2 • > 2 	
HGF protein expression level (if available)	
 • < median • \geq median 	
Age group	
 • < 65 years • \geq 65 years 	
Race	
 • White • Black or African American • Asian • Not collected at this site • Other 	
 • White • Black or African American • Asian • Other (including American Indian or Alaska Native and Native Hawaiian or Other Pacific Islander) 
“Not collected at this site” will be handled as missing

Sex	
 • Male • Female 	
Brain metastases at baseline	
 • Present • Absent 	
ECOG at baseline	
 • 0 • 1 	

9 General Specifications for Data Analyses

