9.5 Conversion Factors

The following conversion factors will be used to convert days into weeks, months or years:

1 week = 7 days, 1 month = 30.4375 days, 1 year = 365.25 days.

If height is recorded in inches, height (cm) = height (in) \times 2.54.

If weight is recorded in pounds, weight (kg) = weight (lb) \div 2.2046.

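### The SAP age formula reduces to consent year minus birth year, so anyone whose birthday falls after consent is reported one year too old and nobody too young

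*SAP*

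**What the plan says.** SAP 11.1 (Demographics, specifications for computation) gives the age in years as "Age = (01.JAN.YEAR informed consent date for screening – 01.JAN.YEAR of birthdate + 1) / 365.25". It adds: "The integer part of the calculated age will be used for reporting purposes". The rule covers every participant; it is not limited to those for whom only a birth year is known. The same section tabulates age as under 65 against 65 and over, with finer bands above 65.

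SAP 8.2 states that "Subgroup analyses will be performed on the primary efficacy endpoint OR and the secondary efficacy endpoints DoR/PFS/OS", and its Table 1 lists the same under-65 / 65-and-over split. The age row has no derivation. For subgroup levels in general, "data as documented in the electronic case report form (eCRF) or provided in the SDTM datasets will be taken".

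Two protocol statements bear on the inputs. Inclusion criterion 1 judges age "at the time of signing the informed consent". Protocol Section 8 says: "Date of birth, sex (gender), race, and ethnicity will be collected only where allowed by local law/regulations".

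**The concern.** The SAP names the consent date as the reference for age and then discards its day and month, although the consent date is known for every treated participant. Moving the birth date back to 1 January as well means that everyone is credited with a birthday that may not yet have happened. The resulting error runs in one direction only.

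This also departs from the SAP's own habits. Durations (SAP 9.4) and times since diagnosis (SAP 11.3) are computed from actual dates. Where only the year of a disease-history date is known and it precedes the treatment year, SAP 9.8 places it at 1 July, not 1 January.

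At stake are the age summaries and, possibly, who counts as 65 or over in the exploratory subgroup analyses of OR, DoR, PFS and OS. Those are run by cohort, with 22 and 20 participants planned.

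**Working it through.** The documents state no figure that depends on this formula, so there is none to reproduce. The check applies the formula literally.

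**Inputs.** Formula and truncation: SAP 11.1. Year length of 365.25 days: SAP 9.5. Planned total at RP2D: 22 + 20 = 42 (Protocol 9.2). Assumed, because the documents do not give them: birthdays uniform over the year; consent dates either spread over the year or fixed on a given day; 2% to 5% of participants aged exactly 64.

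**Step 1: what the formula returns.** For every consent year from 2020 to 2024 and every birth year from 1925 to consent year minus 18, the value exceeds the difference in years by 0.0007 to 0.0048. Its integer part therefore equals consent year minus birth year, with no exceptions.

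**Step 2: one case.** Born 20 November 1956, consent 10 March 2021, true age 64.
- SAP formula: 1 January 1956 to 1 January 2021 is 23,742 days; (23,742 + 1) / 365.25 = 65.005, reported as 65.
- Actual dates: 23,486 days; (23,486 + 1) / 365.25 = 64.30, reported as 64.

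**Step 3: how many are affected.** The overstated share is the part of the year remaining after consent.

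| Consent date (2021) | Reported one year too old | Reported too young |
|---|---|---|
| 15 January | 96% | 0% |
| 15 March | 80% | 0% |
| 15 June | 54% | 0% |
| 15 September | 29% | 0% |
| 15 December | 4% | 0% |
| Four dates in each month | 51% | 0% |

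At one half, that is 42 × 0.5 = 21 participants, and the mean age rises by about half a year.

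**Step 4: the cut at 65.** The same shares apply to true 64-year-olds; no one truly 65 or over drops below the cut. With a proportion s aged exactly 64 and half of them overstated:
- Expected number moved = 42 × s × 0.5: 0.42 for s = 2%, 1.05 for s = 5%.
- Chance of at least one = 1 − (1 − 0.5s)^42: 1 − 0.99^42 = 34%, and 1 − 0.975^42 = 65%.
- By cohort, the expected number is 0.22 to 0.55 of 22 and 0.20 to 0.50 of 20.

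**Step 5: effect on a subgroup rate.** Take 3 responders of 10 as an illustration. Adding one responder gives 4/11 = 36.4% (+6.4 points). Removing one gives 2/9 = 22.2% (−7.8 points). The exact 95% interval for 3/10 is 6.7% to 65.2%.

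**Step 6: the alternatives.**
- Full dates, truncated: about 0.2% are one year too high (consent right at the birthday) and none too low.
- Full consent date with 1 July of the birth year: write consent and birthday as uniform fractions V and U of the year. Age is too high when V ≥ 0.5 and U > V, and too low when V < 0.5 and U ≤ V. Each has probability 1/8, so 12.5% are wrong each way and 25% in all.

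**The case against.** The strongest reply is privacy. Protocol Section 8 makes collection of the birth date subject to local law. Appendix 2 lists it among the site's source records and says that no identifiable information goes to the sponsor. A formula keyed to birth year is what one would write for a database that holds only the year. A reader might infer that the sponsor holds day and month of birth and throws them away; the documents do not show that, and this part of the objection stands. It does not rescue the formula. The SAP does not limit the rule to year-only records, and even with the year alone, dropping the day and month of consent creates a one-way error that could be avoided.

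A reader might also infer that 64-year-olds will enter the efficacy subgroup of 65 and over. The documents do not support that. Table 1 takes its levels from eCRF or SDTM data and gives no age derivation, so the subgroup may rest on a different age. Even if it rests on this one, the chance that nobody crosses is 35% to 66% under the assumptions above.

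Nor should one claim that a misplaced participant typically shifts a subgroup response rate by 10 points. The person moved must be a responder, the denominator moves too, and the shifts in Step 5 are small beside the interval. The subgroups are exploratory and nothing is tested.

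Lastly, the 1 July fallback leaves a quarter of year-only ages wrong by a full year, and two derivations make the cut slightly different between countries, whereas the current rule is uniform. Both points are fair; they are reasons to flag year-only records, not to keep a one-way error.

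**Conclusion.** The formula is wrong as written, at minor severity. That reported age equals consent year minus birth year, that the error is only ever upward, and that it is exactly one year follow from the formula itself and need no assumption.

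The share affected does depend on assumptions: about half if birthdays and consent dates are spread over the year, and anywhere from about 4% to 96% for consent dates between mid-December and mid-January. The crossing at 65 is conditional on Table 1 using this age and on the assumed 2% to 5% aged exactly 64; it then amounts to about one person or none in expectation.

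The certain consequence is an upward shift in the demographic age tables. Eligibility is judged at signing. Overall ORR, the futility rule and the sample size do not use this age. A separate gap is that the demographics table and the age subgroup could disagree, because the SAP does not say that they share one age.

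**What to change.** In SAP 11.1, replace the formula and use the full informed consent date throughout:
- Where the full birth date is held: age = integer part of [(consent date − date of birth + 1) / 365.25].
- Where only the birth year is held: the same formula with 1 July of the birth year, in line with the convention in SAP 9.8. Flag these records.
- State in SAP 11.1 and Table 1 that this one age is used for both the demographics table and the split at 65.

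The cost is a small text change before database lock and some programming; no new data are needed. The remaining weakness lies in year-only records. The fallback removes the directional bias when consent dates are spread over the year, but about 25% of those integer ages will still be wrong by one year, about 12.5% each way. The flag lets a reader see how many participants that concerns.
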